CONFIDENTIAL

A single-centre, open-label, phase I trial evaluating the pharmacokinetics of single ascending oral doses of IRL757 in healthy elderly volunteers.**PROTOCOL SYNOPSIS**

Version: 2.1
Version date: 02-OCT-2024
Superseded version: Not applicable
Sponsor: Integrative Research Laboratories Sweden AB (IRLAB)
Product: IRL757 [REDACTED]
Trial Number(s): IRL757C002
EU trial no: 2024-515124-36-00
NCT no: NCT06699628

Integrative Research Laboratories Sweden AB (IRLAB)
[name]
[name]
SWEDEN
[contact]

TRIAL SYNOPSIS

Trial Title	
A single-centre, open-label, phase I trial evaluating the pharmacokinetics of single ascending oral doses of IRL757 in healthy elderly volunteers.	
Trial code	EU trial no
IRL757C002	2024-515124-36-00
Trial period	Phase of development
Estimated date of first subject enrolled: Q3 2024	Phase I
Estimated date of last subject completed: Q4 2024	
Trial background	
IRL757 [REDACTED] is a novel small molecule compound developed for the treatment of apathy in neurodegenerative disorders. This is a trial of IRL757 with the aim to study safety, tolerability and PK following single oral doses to healthy elderly volunteers.	
Trial design and trial population	
An open label single oral dose trial in elderly healthy volunteers.	
Objectives	
Primary objective: 
 To determine the single oral dose pharmacokinetic (PK) characteristics of IRL757 and its 3 main metabolites in healthy elderly volunteers. 	
Secondary objectives: 
 To evaluate the safety and tolerability of IRL757 after single oral dosing in healthy elderly volunteers. 	
Exploratory objective: 
 To characterize the metabolite profile in plasma and urine of healthy elderly volunteers. 	
Endpoints	
Primary endpoints: PK assessments 
 AUC_{0-t}, AUC_{0-24h}, $AUC_{0-\infty}$, C_{max}, T_{max}, λ_{z}, $T_{1/2}$, amount excreted in urine (Ae), CL/F, V_z/F, fraction of the dose excreted in urine (Fe) (for IRL757), renal clearance CL_R. Dose proportionality after single doses based on AUC_{0-t}, $AUC_{0-\infty}$ and C_{max}. 	
Secondary endpoints: Safety assessments 
 Frequency, seriousness and intensity of Adverse Events (AEs) Physical examination 	

- Columbia-Suicide Severity Rating Scale (C-SSRS)
- Electrocardiogram (ECG) recordings
- Vital signs (blood pressure, heart rate and body temperature)
- Safety laboratory measurements

Exploratory endpoints:

- Metabolite profile in plasma
- Profile of excreted metabolites in urine

Number of subjects planned

12 healthy subjects will be included in two dose groups.

Diagnosis and main eligibility criteria

Healthy elderly volunteers ≥ 65 and < 90 years of age, with a weight of 50 to 110 kg, who are willing to comply with trial procedures and who have given written consent, will be considered eligible for participation in the trial.

Methodology

Twelve (12) eligible and consenting subjects will be allocated to two dose groups. All subjects will be assigned to a single dose treatment with IRL757, 6 subjects to dose 1 and 6 subjects to dose 2.

Eligible subjects will be confined to the research clinic from the evening before first dosing (Day -1) until 48 hours following dosing. The subjects should be fasting overnight (10 hours) before dose administration on Day 1. A Follow-up Visit will be performed 5-10 days after administration of IMP.

Investigational Medicinal Products (IMP), dosage and mode of administration

IRL757 half-life is expected to be 4-10 hours.

IRL757 capsules**Duration of treatment**

Subjects included in the study will receive one dose of IRL757.

Duration of each subject's involvement in the trial

Subjects will be screened for eligibility according to trial-specific inclusion/exclusion criteria at Visit 1 (Screening visit) within 28 days prior to IMP administration.

A Follow-up Visit will be performed for all subjects 5-10 days after last administration of IMP.

Statistical methods

No formal sample size calculation has been performed for this trial. The size of the dose group is considered sufficient to provide adequate information on the safety and PK parameters for the purpose of this trial.

All statistical calculations will be performed using the SAS® version 9.4 or later (SAS Institute Inc., Cary, NC, USA). The statistical analyses will only include descriptive statistics reflecting the explorative nature of the trial. In general, the data will be presented by dose group.

Continuous data will be summarised by dose group using number of observations, mean, standard deviation (SD), median, minimum and maximum. Categorical data will be summarised by dose group using the number and percentage of subjects in each category.

Unless otherwise stated, statistical evaluations will be based on all subjects who have received treatment with IMP. The Full Analysis Set (FAS) data set will be used for the safety, tolerability assessments and description of trial population.

The Pharmacokinetic Analysis Set (PKAS) comprises data from all subjects who received IMP, who provided an evaluable plasma concentration profile and who have no AEs or protocol deviations judged to affect the PK analysis. Individual PK values may be excluded from the analysis as specified in the SAP.

The PK parameters will be calculated by non-compartmental analysis (NCA) using the software Phoenix WinNonlin® version 8.3 or later (Certara, USA).

Table 1 Schedule of events

Visit	Visit 1		Visit 2			Follow-up Visit 5-10 days after IMP administration	
	Screening	In-clinic					
		-28 to -1	-1	1	2		
Informed consent	X						
Demographics and medical/surgical history	X						
Inclusion/exclusion criteria	X		X ¹				
Physical examination	X		X ¹		X ²	X	
C-SSRS	X				X	X	
Weight, BMI	X						
Height	X						
Blood pressure, heart rate, respiratory rate	X	X	X ³	X ³	X	X	
Body temperature		X		X	X		
Haematology, clinical chemistry, coagulation	X	X			X	X	
Urinalysis		X					
HIV, Hepatitis B and C	X						
Drugs of abuse	X	X					
Alcohol screen	X	X					
ECG	X	X ⁶	X ⁴	X ⁴	X ⁴	X	
IMP administration			X				
Blood sampling (PK and metabolite pattern)			X ⁷	X ⁸	X ⁸		
PK urine sampling ⁹			X	X	X		
Baseline symptoms	X	X	X ¹				
AE reporting			X ⁵	X	X	X	
Concomitant medications	X	X	X	X	X	X	
Admission to clinic		X					

¹Pre-dose.

²Symptom-driven physical examination

³Pre-dose and 30 min, 1, 2, 4, 8, 12 and 24 hours post-dose.

⁴Pre-dose, 1, 2, 3, 6, 12, 24 and 48 hours post-dose.

⁵Post dose.

⁶Triplicate ECGs separated by at least 1 min.

⁷Within 60 min pre-dose and 20 (±2) min, 40 (±4) min, 1 hour (±6 min), 2 hours (±12 min), 3 hours (±18 min), 4 hours (±24 min), 6 hours (±30 min), 8 hours (±30 min), 10 hours (±30 min), and 12 hours (±30 min) post-dose.

⁸24 hours (±1 hour) post-dose and 48 hours (±1 hour) post-dose.

⁹Urine collection in fractions 0-6, 6-12, 12-24, 24-36 and 36-48 h post-dose. Subjects to empty their bladder prior to dose for urine collection (a pre-dose sample will be retained). A sample (approx. 2mL) from each fraction will also be kept for metabolite pattern analysis.

Table 2 Detailed schedule of events

Visit No.	Day	Visit 2													Day 2	Day 3
		Day 1														
Time /assessment	Admission	Pre-dose	0	20min	30min	40min	1 h	2 h	3 h	4 h	6 h	8 h	10h	12 h	24 h	48 h
Inclusion/exclusion criteria		X														
Physical examination		X														X ¹
C-SSRS																X
Blood pressure, heart rate, respiratory rate	X	X			X		X	X		X		X		X	X	X
Body temperature	X															X X
Haematology, clinical chemistry, coagulation	X															X
Urinalysis	X															
Drugs of abuse	X															
Alcohol screen	X															
ECG	X ²	X ³					X	X	X		X			X	X	X
IMP administration			X													
Blood sampling ^{4, 6} (PK and metabolite pattern analysis)		X		X		X	X	X	X	X	X	X	X	X	X	X
PK urine sampling ⁵		X														
Baseline symptoms	X	X														
AE reporting									X							X
Concomitant medications	X	X							X							X

¹ Symptom-driven physical examination.

² Triplicate ECGs separated by at least 1 min at Day -1.

³ Within 60 min prior to dose at Pre-dose.

⁴ Within 60 min pre-dose and 20 (±2) min, 40 (±4) min, 1 hour (±6 min), 2 hours (±12 min), 3 hours (±18 min), 4 hours (±24 min), 6 hours (±30 min), 8 hours (±30 min), 10 hours (±30 min), 12 hours (±30 min), 24 hours (±1 hour) and 48 hours (±1 hour) post-dose.

⁵ Urine collection in fractions 0-6, 6-12, 12-24, 24-36 and 36-48 h post-dose. Subjects to empty their bladder prior to dose for urine collection (a pre-dose sample will be retained). A sample of approx. 2 mL from each fraction will also be kept and divided into 2 aliquots for metabolite pattern analysis.

⁶ Plasma obtained at each time point will be divided into two samples, one for PK analysis and one for metabolite pattern analysis. Each of these samples will be separated into two aliquots.

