5.4 Definition of baseline

Baseline is defined as the latest measurement prior to IMP exposure.

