9.2 Analysis of secondary endpoints

9.2.1 Adverse Events (AEs)

AEs and serious AEs (SAEs) will be recorded from the time when informed consent is obtained until the Follow-up Visit. AEs that occur before first treatment with IMP (baseline symptoms) will be listed separately.

All AEs will be described in terms of the dose at which they occurred. AEs will be summarised by System Organ Class (SOC) and Preferred Term (PT) using the Medical Dictionary for Regulatory Activities (MedDRA) vocabulary. The number of subjects reporting AEs, and the number of AEs reported will be presented. The events will be tabulated by SOC, PT and by severity and relationship to IMP. SAEs will be presented in the same tabulations.

9.2.2 *Physical examinations*

Normal and abnormal findings will be specified and summarised by dose group.

9.2.3 *Electrocardiogram (ECG)*

All continuous ECG data will be listed for each subject and summarised by dose group. In addition, ECGs will be categorised as "normal", "abnormal, not clinically significant", or "abnormal, clinically significant" (as judged by the Investigator) and summarised by dose group.

9.2.4 *Vital signs*

Vital signs (blood pressure, heart rate, respiratory rate and body temperature) will be summarised by dose group.

9.2.5 *Safety laboratory analyses*

Safety laboratory data will be summarised by dose group. Safety laboratory interpretations will be summarised by dose groups using frequency tables.

9.2.6 *Columbia-Suicide Severity Rating Scale (C-SSRS)*

This rating scale will be administered for screening of suicidal ideation and behaviour throughout the trial. No formal statistical analysis of the outcome will be performed, i.e., the data will be listed only. Any abnormal findings will be listed and treated as AEs or SAEs.

9.3 *Analysis of exploratory endpoints*

The analysis and results pertaining to the exploratory endpoints, plasma and urine metabolite profiles, will be detailed in a separate report, and hence are not covered in this SAP.

9.4 *Description of trial population*

9.4.1 *Disposition*

A subject disposition will be presented showing the number of screened subjects; the number of withdrawn subjects prior to dose, including the reason for withdrawal; the number of included subjects in each dose group; the number of withdrawn subjects, including the reason for withdrawal; the number of completed subjects; the number of subjects included in the analysis sets, and the number of subjects at each visit.

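### Body temperature has no Day 1 reading, so no scheduled measurement can show an acute effect near peak exposure, and its within-group change from baseline is mixed with time of day

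*Protocol*

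**What the plan says.** The protocol synopsis, under secondary endpoints, lists "Vital signs (blood pressure, heart rate and body temperature"). SAP 9.2.4 carries this into the analysis: "Vital signs (blood pressure, heart rate, respiratory rate and body temperature) will be summarised by dose group".

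The schedule treats temperature differently from the other vital signs:

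- **Blood pressure, heart rate, respiratory rate.** Table 1 (with its footnote 3) and Table 2 place these at admission, pre-dose, 30 min, 1, 2, 4, 8, 12 and 24 h, and again at 48 h.
- **Temperature.** In Table 1 the "Body temperature" row is marked at Day -1, Day 2 and Day 3, with Day 1 blank. In Table 2 it is marked at admission and then twice at the end of the row (24 h and 48 h), with nothing pre-dose or from 0 to 12 h.

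Three statements fix the timing. On confinement: "Eligible subjects will be confined to the research clinic from the evening before first dosing (Day -1) until 48 hours following dosing". On fasting: "The subjects should be fasting overnight (10 hours) before dose administration on Day 1". On the drug: "IRL757 half-life is expected to be 4-10 hours".

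SAP 5.4 states: "Baseline is defined as the latest measurement prior to IMP exposure". SAP section 9 adds 95% CIs for vital signs. The Table VS 1 shell shows measured value, change and relative change from baseline for each dose group. Group size is "6 subjects to dose 1 and 6 subjects to dose 2", and there is no placebo arm.

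**The concern.** Two consequences follow from the empty Day 1 cells.

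First, the period of highest exposure passes without a thermometer reading. A transient rise or fall in the first 12 hours would go unmeasured, although staff are already at the bedside taking the other vital signs.

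Second, with no pre-dose reading on Day 1, the SAP 5.4 baseline for temperature falls back to the admission value from the evening before. The post-dose values are taken 24 h and 48 h after dosing, that is, at the clock time of dosing. The printed change therefore combines any drug effect with any evening-to-dosing-time difference, and without placebo subjects nothing in Table VS 1 separates the two. At stake is a change row with a confidence interval that a reader of the trial report could take for a drug effect.

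**Working it through.** The plan gives no sample size, SD or expected difference for this endpoint, so there is no stated figure to reproduce.

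**1. Schedule, by column position.** In the Table 1 row for blood pressure, heart rate and respiratory rate, the entries run screening, Day -1, Day 1, Day 2, Day 3, follow-up, all filled. The temperature row, read against the same columns, is blank, X, blank, X, X, blank. The last two marks in the Table 2 row are run together in the extracted text, but they agree with Table 1.

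**2. Which reading is the baseline.** The latest temperature before dosing is the Day -1 admission value. Admission is in the evening.

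**3. Clock time of the post-dose readings.** The 24 h and 48 h readings fall at the clock time of dosing, which is not stated. A 10-hour overnight fast points to morning. Both tables also place the 12 h sample within Day 1, which on a calendar-day reading puts dosing at noon or earlier. Morning is therefore an inference, though a reasonable one.

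**4. Exposure left at the first post-dose reading.** Fraction remaining = 2^(-t / half-life), mono-exponential and counted from time zero.

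| Half-life | 24 h | 48 h |
|---|---|---|
| 4 h | 2^(-6.0) = 1.6% | 2^(-12) = 0.02% |
| 10 h | 2^(-2.4) = 18.9% | 2^(-4.8) = 3.6% |

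**5. Width of the interval.** With n = 6 (5 df), the 95% CI half-width is 2.571 / √6 = 1.05 times the SD of the change.

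**6. Chance that the CI excludes zero from a clock-time shift alone.** Let δ be the shift and σ the SD of change. The mean change divided by its standard error follows a noncentral t with 5 df and noncentrality δ√6/σ. The probability is P(t > 2.571) + P(t < -2.571). *Neither δ nor σ is in the documents. Both are assumed to lie between 0.2 and 0.5 °C.* For example, δ = σ = 0.3 gives noncentrality 2.449 and a probability of 50.7%.

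| SD of change | δ = 0.2 °C | δ = 0.3 °C | δ = 0.5 °C |
|---|---|---|---|
| 0.2 °C | 50.7% | 83.3% | 99.7% |
| 0.3 °C | 26.5% | 50.7% | 89.9% |
| 0.4 °C | 17.1% | 32.1% | 68.9% |
| 0.5 °C | 12.7% | 22.4% | 50.7% |

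With δ = 0 the figure is 5%. Under these assumptions the range is about 13% to 99.7%, for each dose group and each post-dose time.

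**The case against.** A reader might infer that temperature, as scheduled, cannot show a drug effect at all. The documents do not support that. Up to about 19% of parent drug remains at 24 h. That figure counts decay from time zero; if the peak came at 3 h (an assumption), a 10 h half-life would leave 2^(-21/10) = 23% of the peak. No half-life is stated for the three main metabolites. A delayed or sustained effect could therefore appear at 24 h, and AE reporting on Day 1 would still pick up symptomatic events.

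The time-of-day argument is also softer than its arithmetic suggests. No clock time is given, only the protocol synopsis is available, and the full protocol may specify one. The existence, direction and size of a diurnal shift come from outside the documents, so the percentages depend almost wholly on the assumed inputs.

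No decision hangs on the interval either. The protocol describes its analyses as descriptive, and the only hypothesis named in SAP 5.1 is dose proportionality, judged with 90% CIs. Table VS 1 also prints measured values, so 24 h and 48 h can be compared with each other at the same nominal clock time. A shift common to both groups would not bias a between-dose contrast.

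All of this stands, and it limits the severity. It does not remove the point. The Day 1 cells are empty in both tables, no reason is given, no between-dose contrast is tabulated, and the change row that is tabulated carries the mismatch.

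**Conclusion.** The point holds in a limited form, as a minor one. No scheduled reading can show an acute temperature effect around peak exposure. The within-group change in Table VS 1, with its 95% CI, is confounded with time of day.

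The first conclusion rests on the schedule and on the stated half-life, with mono-exponential decay of the parent (1.6-19% left at 24 h). The second rests on SAP 5.4 and the evening admission, plus the inference that dosing is in the morning. Its size cannot be fixed from the documents: 13% to 99.7% against a nominal 5%, for an assumed shift and SD of 0.2-0.5 °C each. The interval is descriptive, so the harm is a misreading of the table rather than a wrong trial decision. It would also go too far to conclude that the change rows must be dropped. They still allow an informal comparison between doses that a common shift does not bias, although with 6 per group it is imprecise.

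**What to change.** In Tables 1 and 2, add body temperature to the Day 1 pre-dose vital-signs set. SAP 5.4 then selects that reading as baseline without any change of wording, and it matches the clock time of the 24 h and 48 h readings. Also add temperature at one or more post-dose vital-sign times already scheduled within 12 h (30 min, 1, 2, 4, 8 or 12 h). The pre-dose reading alone would repair the baseline but not the gap around peak exposure.

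The cost is a few thermometer readings per subject when staff are already measuring blood pressure, and a small schedule amendment. No extra visit or blood sample is needed.

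If the data are already collected, keep both the measured values and the change rows. Add a footnote to Table VS 1 saying that the temperature baseline is an evening reading and that within-group change must not be read as a drug effect. If the sparser schedule was deliberate, state the reason.

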3 LIST OF ABBREVIATIONS AND DEFINITION OF TERMS

| Abbreviation | Explanation |
|-----------------------|--|
| ADaM | Analysis Data Model |
| AE | Adverse event |
| A _e | Amount excreted in urine |
| ATC | Anatomical therapeutic chemical |
| AUC | Area under the plasma concentration vs. time curve |
| AUC _{0-inf} | AUC from 0 to infinity |
| AUC _{0-last} | AUC from 0 to time of last measurable plasma concentration |
| BLQ | Below lower limit of quantification |
| BMI | Body mass index |
| CDISC | Clinical Data Interchange Standards Consortium |
| CI | Confidence interval |
| CL/F | Apparent total body clearance following extravascular administration |
| CL _R | Renal clearance |
| C _{max} | Maximum observed concentration |
| C-SSRS | Columbia-Suicide Severity Rating Scale |
| [REDACTED] | [REDACTED] |
| CTP | Clinical trial protocol |
| CV | Coefficient of variation |
| DDP | Data display plan |
| ECG | Electrocardiogram |
| eCRF | Electronic case report form |
| FAS | Full analysis set |
| FDA | United States Food and Drug Administration |
| F _e | Fraction of the dose excreted in urine |
| FIH | First-In-Human |
| Geo | Geometric |
| IG | Implementation guideline |
| IMP | Investigational medicinal product |
| lambda _z | Terminal elimination rate constant |
| lin | Linear |
| LLOQ | Lower limit of quantification |

| Abbreviation | Explanation |
|-------------------|--|
| log | Logarithmic |
| Max | Maximum |
| MedDRA | Medical dictionary for regulatory activities |
| Min | Minimum |
| NA | Not applicable/not available |
| NC | Not calculated |
| NCA | Non-compartmental analysis |
| PK | Pharmacokinetic(s) |
| PKAS | PK analysis set |
| PT | Preferred term |
| SAE | Serious adverse event |
| SAP | Statistical analysis plan |
| SAS | Statistical analysis system |
| SD | Standard deviation |
| SDTM | Trial data tabulation model |
| SOC | System organ class |
| T _{last} | Time of occurrence of last observed plasma concentration |
| T _{max} | Time of occurrence of C _{max} |
| T _{1/2} | Terminal elimination half-life |
| ULOQ | Upper limit of quantification |
| V _{z/F} | Volume of distribution (associated with terminal phase) following extravascular administration |
| WHO | World Health Organization |

4 INTRODUCTION

This Statistical analysis plan (SAP) gives a detailed description of the planned statistical analysis for trial IRL757C002.

4.1 Trial design

This is a single-centre, open-label, phase I trial evaluating the pharmacokinetics (PK) of single ascending oral doses of IRL757 in healthy elderly volunteers.

The trial will be a parallel group design with one (1) pre-defined starting dose [REDACTED] and one ascending dose level of IRL757 [REDACTED]

Please see the clinical trial protocol (CTP) for additional details.

4.2 Trial objectives and endpoints

Table 1 Trial objectives and endpoints

| Objectives | Endpoints | Assessments | Analyses | Data display plan (DDP) |
|---|---|--|---|---|
| Primary objective | Primary endpoints | | | |
| To determine the single dose PK characteristics of IRL757 and its 3 main metabolites in elderly healthy volunteers. | 
IRL757 and 3 main metabolites: Area under the plasma concentration-time curve AUC_{0-t}, AUC_{0-24}, $AUC_{0-\infty}$, maximum concentration (C_{max}), time to maximum concentration (T_{max}), terminal elimination rate constant (λ_{z}), terminal half-life ($T_{1/2}$), amount excreted in urine (A_e)
 
IRL757 only: total apparent clearance of drug from plasma (CL/F), volume of distribution (V_z/F), fraction of the dose excreted in urine (F_e), renal clearance CL_R.
 | PK plasma and urine sampling | Descriptive statistics, Section 9.1.1 | Sections 10.2.2.1, 10.3.1.1 |
| | 
IRL757 and metabolites M5, M7: Dose proportionality after single oral doses based on AUC_{0-t}, $AUC_{0-\infty}$ and C_{max}
 | | Dose proportionality analysis, Section 9.1.1.1 | Section 10.3.1.2 |
| Secondary objective | Secondary endpoints | | | |
| To evaluate the safety and tolerability of IRL757 after single oral dosing in healthy elderly volunteers. | 
Frequency, seriousness and intensity of adverse events (AEs).
 
Physical examination
 
Electrocardiogram (ECG) recordings
 
Vital signs
 
Safety laboratory measurements
 
Columbia-Suicide Severity Rating Scale (C-SSRS)
 | 
AE reporting and questioning
 
Physical examinations
 
12-lead safety ECG
 
Blood pressure, heart rate, respiratory rate, body temperature
 
Blood sampling for haematology, clinical chemistry and coagulation
 
C-SSRS questionnaire
 | 
Descriptive statistics, Section 9.2.1
 
Descriptive statistics, Section 9.2.2
 
Descriptive statistics, Section 9.2.3
 
Descriptive statistics, Section 9.2.4
 
Descriptive statistics, Section 9.2.5
 
Listings, Section 9.2.6
 | 
Section 10.2.3.1
 
Section 10.2.3.2
 
Section 10.2.3.3
 
Section 10.2.3.4
 
Section 10.2.3.5
 
Section 10.4
 |
| Exploratory objective | Exploratory endpoints | | | |

| Objectives | Endpoints | Assessments | Analyses | Data display plan (DDP) |
|--|--|-----------------------------------|--|-------------------------|
| To characterize the metabolite profile in plasma and urine in healthy elderly volunteers and compare with the profiles observed in healthy volunteers of the First-In-Human (FIH) study. | Metabolite pattern analysis in plasma in comparison with the metabolite profile in plasma from the FIH study Profile of excreted metabolites in the urine | Plasma sampling Urine sampling | The analyses and results pertaining to the exploratory endpoints, plasma and urine metabolite profiles, will be detailed in a separate report and hence are not covered in this SAP. | |

